The "X" in the table denotes the assessments to be recorded in the clinical database or received electronically from a vendor. The "S" in the table denotes the assessments that are only in the participant's source documentation and do not need to be recorded in the clinical database.

As per Section 3.9, during a Public Health emergency as declared by Local or Regional authorities i.e. pandemic, epidemic or natural disaster that limits or prevents on-site study visits, alternative methods of providing continuing care may be implemented by the investigator as the situation dictates. If allowable by a local Health Authority and depending on operational capabilities, phone calls, virtual contacts (e.g. tele consult) or visits by site staff/ home nursing staff to the patient's home, can replace on-site study visits, for the duration of the disruption until it is safe for the patient to visit the site again.

Novartis Confidential Page 110
Amended Protocol Version 11 (clean) Protocol No. CLMI070X2201

Table 7-1 Assessment Schedule – Part 1 – Initial treatment period (Day -14 to Day 85)

	Screening	Baseline	Baseline Cont.				Treat	tment	Peri	od 1							Т	reatm	ent Pe	eriod 2			
Visit Numbers (internal use only) 1	1	2	3			4		I	5	6	7	8	9	10	11	12	13	14	15	16	17	18	19
Day	D -14 to -8	D -7 to -3	D-2 to -1			1			2	3	5	8	15	22	29	36	43	50	57	64	71	78	85
Week	-	-	-				1					2	3	4	5	6	7	8	9	10	11	12	13
Time (h)	-	-	-	0	1	2	4	8	24	48	96	168	-	-	-	-	-	-	-	-	-	-	-
Obtain informed consent	Х																						
Inclusion /Exclusion criteria	X	Х																					
Relevant med history / current medical conditions	X																						
SMN2 copy number ³	X ³																						
Demography	X																						
Physical examination	X			Х								Х	Х	Х	X⁴	Х	Х	Х	X⁴	Х	Х	Х	X ⁴
Hepatitis and HIV screen	×																						
Drug administration				Х									Х	Х	Х	Х	Х	Х	Х	Х	Х	Х	Х
Vital signs and body measurements																							
Body weight/ Body length/ BSA	X			X								Х	Х	Х	Х	Х	Х	Х	Х	Х	Х	Х	Х
Head & Chest Circumference	X			Х								Х	Х	Х	Х	Х	Х	Х	Х	Х	Х	Х	Х
Bodytemperature	X			Х		Х			Х	Х	Х	Х	Х	Х	Х	Х	Х	Х	Х	Х	Х	Х	Х
Blood pressure / Pulse rate/ Respiratory rate	X			Х		Х			Х	Х	Х	Х	Х	Х	Х	Х	Х	Х	Х	Х	Х	Х	Х
ECG evaluation	Х					Х						Х											Х
Echocardiogram	Х														Х				Х			Х	
Hematology, Blood chemistry, Urinalysis	Х		Х							Х		Х	Х		Х		Х		Х		Х		Х
Ophthalmologic examination		Х																				Х	

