2.1.1 General definitions

‘**Actual dose**’ will be derived as the current dose for each subject on a daily basis across the entire study; in the case of the day of a dose change, the new dose will be used.

‘**Treatment group**’ in Parts 2 & 3 will refer to the treatment group combination (as mentioned above) for efficacy analyses, and to the actual treatment for safety analyses (see definition below). In Parts 1 & 3, this will be Overall.

‘**Cohort**’ will refer to the initial dose for baseline or demographic characteristics.

The term ‘**Study Day**’ in this document relates to the Analysis Relative Day, Relative Start Day or Relative End Day as applicable. ‘**Study Day**’ is defined relative to the analysis reference date, which is the date of treatment assignment; it is the number of days from the reference date to the analysis date. For all dates on or after the analysis reference date, the study day is the difference to the analysis reference date plus one day (i.e. for date \geq reference date, study day = date - reference date + 1); for any dates prior to the analysis reference date, the study day is

simply the difference to the reference date (i.e. for date < reference date, study day = date - reference date). Thus, the Subject Reference Start Date is designated as Study Day 1, while the date directly prior to the reference date is defined as Study Day -1 (there is no Study Day 0).

'Baseline' is the last non-missing assessment obtained prior to the first administration of study drug. That means that if the measurement at the baseline visit is missing, then the previous measurement preceding baseline will be used as the baseline measurement. For pulse and blood pressure vital sign values, the baseline is the last non-missing value taken prior to the first administration of study drug.

'Treatment phase' includes the time interval on treatment and post-treatment follow-up. Any measurements taken after baseline will be considered as post-baseline measurements.

'Actual treatment' is defined as the treatment group the patient has most exposure to in each Part (for Parts 2 & 3), leading to a treatment group combination; in the case of two treatments having identical exposure, the higher dose will be used. This will be used for safety analyses.

'Calendar age' is defined as the age at the date of evaluation.

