2.1.2 Visit windows

Visit-windows will be used for both efficacy and safety data summaries by visit. Visit windows define a time period "around" the targeted visit date as defined in the evaluation schedule of the clinical study protocol. Visit-windows are non-overlapping and defined without gaps between consecutive visit windows. The width of visit windows may vary over the course of the study period.

The purpose of visit windows is to analyze data based on the actual study days (rather than "nominal" visits). E.g., if a subject's Week 3 visit is delayed; it is possible that the Week 3 data be re-aligned to visit-window Week 5 and be summarized under Week 5.

- For **efficacy analyses** all nominal visits (i.e. excluding unscheduled visits) will be mapped into one of the defined visit-windows.
- For **safety analyses** all nominal visits (i.e. excluding unscheduled visits) will be mapped into one of the defined visit-windows. Data from unplanned visits and unscheduled visits will not be re-mapped to other visits for the purpose of displaying variables over time except for laboratory data. For laboratory data, a time window will be used to identify the assessment closest to the target day within the window over time. The unplanned and unscheduled visits will be used in the analysis of event endpoints, and will be counted towards shift tables or other analyses regarding the worst observed values for patients.

It is possible that more than one assessment of a subject fall into a particular visit-window. [Section 2.1.3](#), deals with the statistical approaches to handle multiple visits in a given visit-window.

Tables displaying summary statistics “by visit” will also use the term *visit-window* as column header; this is to remind the reviewer that multiple assessments of a subject might be summarized. [Table 2-1](#) up to Table 2-12, provide visit-windows definitions for applicable parameters in Part 1 and Part 2.

In all scenarios, later visits in Part 1, Part 1 & 3 and/or visits in Parts 2 & 3, will be treated in a similar fashion to those displayed, so that days between visits are divided evenly, without any gaps. The target day is number of weeks * 7 – 6. For Part 1, after week 26 visit, the extended treatment period (as per protocol Table 7-2) is repeated. For example, for CHOP-INTEND, after week 26 visit, there are week 32 (+6 weeks) and week 39 (+7 weeks) visits.

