Week 45	292	309	333	288	309	333
Week 52	334	358	382	334	358	382

Table 2-5 Visit windows for ECG evaluations

Visit-window	Part 1 Day			Part 2 Day		
	Start	Target	End	Start	Target	End
Day 1	1	1	1	1	1	1
Week 2	2	8	46	2	8	46
Week 13	47	85	130	47	85	99
Week 17				100	113	145
Week 26	131	176	221	146	176	190
Week 30				191	204	236
Week 39	222	267	312	237	267	281
Week 43				282	295	326
Week 52	313	358	403	327	358	389

Table 2-6 Visit windows for body temperature and blood pressure/pulse rate/respiratory rate

Visit-window	Part 1 Day			Part 2 Day		
	Start	Target	End	Start	Target	End
Day 2	1	2	2	1	2	2
Day 3	3	3	3	3	3	5
Day 5	4	5	6			
Week 2	7	8	11	6	8	18
Week 3	12	15	18			
Week 4	19	22	25			
Week 5	26	29	32	19	29	43
Week 6	33	36	39			
Week 7	40	43	46			
Week 8	47	50	53			
Week 9	54	57	60	44	57	71
Week 10	61	64	67			
Week 11	68	71	74			
Week 12	75	78	81			
Week 13	82	85	102	72	85	102
Week 18	103	120	134	103	120	134
Week 22	135	148	162	135	148	162
Week 26	163	176	190	163	176	193
Week 31	191	211	225	194	211	225
Week 35	226	239	253	226	239	253
Week 39	254	267	281	254	267	284
Week 44	282	302	316	285	302	316
Week 48	317	330	344	317	330	344
Week 52	345	358	372	345	358	372

[figure not shown]

Table 2-8 Visit windows for physical examination, respiratory function, body weight/body length/BSA, head and chest circumference

Visit-window	Part 1 Day			Part 2 Day		
	Start	Target	End	Start	Target	End
Week 2	1	8	11	1	8	18
Week 3	12	15	18			
Week 4	19	22	25			
Week 5	26	29	32	19	29	43
Week 6	33	36	39			
Week 7	40	43	46			
Week 8	47	50	53			
Week 9	54	57	60	44	57	71
Week 10	61	64	67			
Week 11	68	71	74			
Week 12	75	78	81			
Week 13	82	85	102	72	85	102
Week 18	103	120	134	103	120	134
Week 22	135	148	162	135	148	162
Week 26	163	176	190	163	176	193
Week 31	191	211	225	194	211	225
Week 35	226	239	253	226	239	253
Week 39	254	267	281	254	267	284
Week 44	282	302	316	285	302	316
Week 48	317	330	344	317	330	344
Week 52	345	358	372	345	358	372

Table 2-9 Visit-windows for Ulnar CMAP and mRNA blood collection

[figure not shown]
Visit-window	Part 1 Day			Part 2 Day		
	Start	Target	End	Start	Target	End
Week 13	1	85	130	1	85	130
Week 26	131	176	221	131	176	221
Week 39	222	267	312	222	267	312
Week 52	313	358	403	313	358	403

Table 2-10 Visit-windows for ophthalmological evaluations

Visit-window	Part 1 Day			Part 2 Day		
	Start	Target	End	Start	Target	End
Week 12	1	78	123	1	78	123
Week 25	124	169	214	124	169	214
Week 38	215	260	305	215	260	305
Week 51	306	351	396	306	351	396

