2.1.3 Multiple assessments within visit windows

It is possible that multiple assessments of a subject fall into the same visit-window (e.g. due to unscheduled visits). All results (scheduled and unscheduled) will be displayed in listings, but only one value (observed or derived) will be selected for summary statistics by visit-window.

For **quantitative variables**, the assessment closest to the target day will be selected. If more than one assessment is at the same distance to the target day, the worst case will be selected. For tables displaying the worst-case scenario, all assessments within a visit window will be used to identify the worst (e.g. the maximum or the minimum depending on parameter). For qualitative variables, the worst record is selected; it is noted that in the relevant data subsection, worst case is always well defined.

Table 2-13 Worst case direction for each parameter

[figure not shown]
Assessment	Worst case
CHOP INTEND	The lower the value
HINE	The lower the value
ECGs	The higher the value
Vital Signs	The higher the value
Labs	Usually the higher the value; however for some labs, such as hemoglobin and platelets, both higher and lower values can be worst case direction
Neurophysiological evaluations (NCV, CMAP, etc.)	The lower the value
Growth measurements	The lower the value
Respiratory measurements	The lower the value

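### SAP Table 2-6 has no Day 1 window, so the vital signs scheduled 2 h after the first dose drop out of the by-window summaries or appear under a later day

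*SAP*

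**What the plan says.** Protocol Tables 7-1 (Part 1) and 7-3 (Part 2) mark body temperature and the row "Blood pressure / Pulse rate/ Respiratory rate" on Day 1 at 0 h and 2 h, then at 24 h (Day 2) and 48 h (Day 3).

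SAP 2.1.1 treats the 0 h reading as a candidate baseline, because "the baseline is the last non-missing value taken prior to the first administration of study drug". The 2 h reading is on the other side of that line: "Any measurements taken after baseline will be considered as post-baseline measurements".

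SAP 2.1.2 requires that nominal visits "will be mapped into one of the defined visit-windows". The table for these parameters, "Visit windows for body temperature and blood pressure/pulse rate/respiratory rate", begins with Day 2 = 1/2/2 (start/target/end) in both parts. By contrast, the table "Visit windows for ECG evaluations" gives Day 1 its own window, 1/1/1.

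SAP 2.1.3 then states that "only one value (observed or derived) will be selected for summary statistics by visit-window" and that, for quantitative variables, "the assessment closest to the target day will be selected".

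**The concern.** The SAP's windows are meant to surround the visits in the protocol schedule. Here a scheduled, post-baseline time point has no window of its own and shares one with the next day's visit. Since only one value per window is summarised, one of the two scheduled readings has to give way.

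Vital signs are a primary safety endpoint in all three parts (Protocol 2.1, SAP 1.1.1). Protocol 3.1 and 3.2 place safety assessments before dosing at the later dosing visits of Parts 1 and 2. The first-dose 2 h set is therefore the only one those parts schedule within the first few hours after a dose. Median Tmax is 2.97 to 4.00 h in Part 1 and 3.75 to 4 h in Part 2 (Protocol 1.1.1), so 2 h lies on the rise towards peak. At stake is whether the change-from-baseline tables contain any early post-dose row.

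**Working it through.** **Inputs**
- Schedule (Protocol Tables 7-1 and 7-3): post-dose readings at 2, 24, 48 and 168 h in both parts, plus 96 h in Part 1.
- Windows (SAP Table 2-6), Part 1: Day 2 = 1/2/2, Day 3 = 3/3/3, Day 5 = 4/5/6. Part 2: Day 2 = 1/2/2, Day 3 = 3/3/5.
- Rules (SAP 2.1.2 and 2.1.3): windows do not overlap and leave no gaps, days between targets are split evenly, and the value closest to target is used.

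**Step 1: is the missing row real?** Yes. The Day 2 row itself starts at day 1, so a non-overlapping Day 1 row has no room. Rebuilding the edges as end = floor((target + next target)/2), with next start = end + 1 and the first window starting at day 1, gives floor((2 + 3)/2) = 2 for the first row, which is 1/2/2 as printed. The same rule reproduces all 15 Part 2 rows and 18 of 24 Part 1 rows. The six exceptions (Day 3/5, Week 26/31 and Week 39/44) differ by 1 to 3 days at an edge and do not bear on this point.

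**Step 2: selection when first dose is on Study Day 1**
- 2 h reading: Study Day 1, distance |1 − 2| = 1.
- 24 h reading: Study Day 2, distance |2 − 2| = 0.

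Both sit in the Day 2 window. The 24 h value is selected whenever it exists. If it is missing, the 2 h value is selected and printed under Day 2. The result is the same in both parts.

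**Step 3: what if assignment precedes first dose?** SAP 2.1.1 counts Study Day from treatment assignment, not from first dose, and Protocol 3.2 places a combined baseline/randomization heading over Visits 2 and 3. The documents do not give the actual gap. Assuming 1 or 2 days, which matches Visit 3 at Day -2 to -1:

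| First dose falls on | 2 h reading | Later readings |
|---|---|---|
| Study Day 1 | in Day 2 window; loses to 24 h if present | 24 h under Day 2 |
| Study Day 2 | selected, printed as Day 2 | 24 h printed as Day 3 |
| Study Day 3 | selected, printed as Day 3 | Part 1: 24 h and 48 h share the Day 5 window, 48 h selected. Part 2: both share the Day 3 window and lose to 2 h |

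So the 2 h value is either omitted or given the wrong day. Which of these happens depends on the anchor.

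**Step 4: the repaired table.** Adding a Day 1 target gives floor((1 + 2)/2) = 1, so Day 1 = 1/1/1 and Day 2 = 2/2/2. No row from Day 3 onward needs to change. With first dose on Study Day 1, the 2 h value is summarised under Day 1 and the 24 h value under Day 2. A missing 24 h value leaves Day 2 empty. If first dose falls on Study Day 2, a 1/1/1 row read on the SAP's Study Day would miss the 2 h value, so the row must be keyed to first dose.

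**Number affected:** 13 treated in Part 1 + 25 in Part 2 = 38 at most.

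**The case against.** The strongest objection concerns scope. All vital-sign values are listed with age-dependent abnormalities flagged, and blood pressure and pulse appear in individual panel plots (SAP 2.8.6). Any worst-case table uses every value in a window (SAP 2.1.3). SAP 2.1.2 counts even unscheduled values towards shift tables, so the scheduled 2 h values very probably count there too. Clinically significant findings are also reported as adverse events (SAP 2.8). This stands. A reader might infer that the 2 h data are discarded or that an acute effect could not be seen anywhere in the report; the documents do not support either. The cover is thinner for temperature and respiratory rate, which have neither the panel plot nor reference ranges for the shift table.

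A reader might also connect the gap with the reported SUSARs, because hypertension and sinus tachycardia are among the terms (Protocol 1.1.1). The documents do not tie those events to the hours after a dose. The rationale for Amendment 04 places two serious cardiac events within the first 6 to 8 weeks of treatment and considers causation by the drug unlikely. No link is shown.

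The ECG comparison is not decisive on its own. No ECG is scheduled on Day 2 or Day 3, and a first window starting at day 1 is usual in this SAP (Tables 2-1 and 2-8 to 2-11). In those tables, however, no post-dose Day 1 reading is scheduled, so the convention costs nothing there. For vital signs it does.

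Finally, the gain is modest. All parts are non-confirmatory, Part 1 is summarised without stratifying by dose, and vital signs up to 14 days after dosing were reviewed before each Part 1 escalation (Protocol 3.7). This limits the weight of the point but does not remove the inconsistency between schedule and table.

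**Conclusion.** The point holds for the descriptive by-visit-window tables and no further. With first dose on Study Day 1, every infant with both readings loses the 2 h value from those summaries, and an infant without the 24 h reading has the 2 h value shown as Day 2. With assignment 1 or 2 days earlier, the 2 h value is retained but shown as Day 2 or Day 3. A statement that all 2 h values are lost would need first dose to be on Study Day 1 for every infant, which the SAP's definition of Study Day does not guarantee. No inferential result or sample-size figure is touched. The point is worth correcting because the reading belongs to a scheduled primary safety measurement and the repair is nearly free.

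**What to change.** In SAP Table 2-6:
- Add a row for Day 1, 2 h post-dose, with window 1/1/1, restricted to post-dose records. Identify it by nominal time point or by day relative to first dose rather than by days since treatment assignment. Records placed in this row should not also compete for a later window.
- Change Day 2 from 1/2/2 to 2/2/2.
- Leave Day 3 onward as it is.
- Summarise change from the SAP's existing pre-dose baseline.

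The cost is one added row, one edited row and a re-run of the affected tables. No new data are needed.

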2.1.3 Multiple assessments within visit windows

It is possible that multiple assessments of a subject fall into the same visit-window (e.g. due to unscheduled visits). All results (scheduled and unscheduled) will be displayed in listings, but only one value (observed or derived) will be selected for summary statistics by visit-window.

For **quantitative variables**, the assessment closest to the target day will be selected. If more than one assessment is at the same distance to the target day, the worst case will be selected. For tables displaying the worst-case scenario, all assessments within a visit window will be used to identify the worst (e.g. the maximum or the minimum depending on parameter). For qualitative variables, the worst record is selected; it is noted that in the relevant data subsection, worst case is always well defined.

Table 2-13 Worst case direction for each parameter

[figure not shown]
Assessment	Worst case
CHOP INTEND	The lower the value
HINE	The lower the value
ECGs	The higher the value
Vital Signs	The higher the value
Labs	Usually the higher the value; however for some labs, such as hemoglobin and platelets, both higher and lower values can be worst case direction
Neurophysiological evaluations (NCV, CMAP, etc.)	The lower the value
Growth measurements	The lower the value
Respiratory measurements	The lower the value

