7.4.7 Other safety evaluations

Respiratory function

- Respiratory rate
- Pulse oximetry
- Paradoxical breathing
- Breathing pattern: chest circumference measured during quiet breathing or sleep

Ophthalmologic examination

An ophthalmologic examination without sedation using dilated direct and indirect ophthalmoscopy will be performed at the time points defined in the Assessment Schedule. Any ocular change, compared to baseline or previous assessment that is considered clinically significant will need to be documented and reported as a new AE.

In addition, where feasible, hand-held Optical Coherence Tomography (OCT) will be performed as well at the same time points as the routine ophthalmologic examination, as described in Table 7-1 for the initial treatment period, Table 7-2 for the extended treatment period in Part 1. Please refer to Table 7-3 for Part 2 and Table 7-4 for Part 3. Further details can be found in the Site Operations Manual.

Any ocular change, compared to baseline or previous assessment that is considered clinically significant will need to be documented and reported as a new AE.

Nerve Conduction Studies

Nerve conduction study is a test commonly used to evaluate the function, especially the ability of electrical conduction by the motor and sensory nerves of human body. Nerve conduction

velocity (NCV) and F wave are common measurements made during this test. A NCV test measures how quickly electrical impulses move along a nerve. Velocities will be assessed in upper and lower limbs. The Compound Motor Action Potential (CMAP) is recorded by electrical stimulation of a motor nerve and measured in millivolts.

The Sensory Motor Action Potential (SNAP) is obtained by electrically stimulating sensory fibers and is measured in microvolts.

The **same order** should be followed at all centers, starting from (1) and going as far as patient can tolerate. Numbers with a/b refer to the fact that these measurements are yielded from one and the same stimulation.

The following tests will be assessed as safety parameters:

Nerve conduction study safety parameters

A maximum of 3 measurements are performed per nerves.						
1a	Sural SNAP	Measurement #1 #2 #3	Safety (+)			
1b	Sural sensory NCV	Measurement #1 #2 #3	Safety (+)			
2a	Ulnar CMAP	Measurement #1 #2 #3	Efficacy			
2b	Ulnar motor NCV	Measurement #1 #2 #3	Efficacy			

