2.8.8 Neurophysiological Examination

All neurophysiological evaluations [Ulnar compound motor action potential (CMAP), Ulnar nerve conduction velocity (NCV), Sural SNAP, Sural sensory NCV] will be descriptively summarized and listed.

Furthermore the following analyses will be carried out:

- Spaghetti plot of raw neurophysiological parameters vs months from first dose over time with all raw data (Parts 2 & 3)
- Spaghetti plot of raw neurophysiological parameters vs months from first dose over time excluding implausible post-baseline zero values (Parts 2 & 3)
- Spaghetti plot on a log scale of raw neurophysiological parameters vs months from first dose over time excluding implausible post-baseline zero values (Parts 2 & 3)
- Spaghetti plot on a log scale of normalised neurophysiological parameters vs months from first dose over time with all normalised data (Parts 2 & 3)
- Spaghetti plot on a log scale of normalised neurophysiological parameters vs months from first dose over time excluding implausible post-baseline zero values (Parts 2 & 3)

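### No rule reduces the up to three same-session nerve conduction measurements to one value; kept as separate records, SAP 2.1.3 would take the lowest after dosing but not at baseline

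*SAP*

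**What the plan says.** Protocol 7.4.7 lists sural SNAP, sural sensory NCV, ulnar CMAP and ulnar motor NCV, each with "Measurement #1 #2 #3", under the note "A maximum of 3 measurements are performed per nerves". Testing goes only as far as the child tolerates, so the number obtained can differ between children and sessions.

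SAP 2.1.3 says that "only one value (observed or derived) will be selected for summary statistics by visit-window". Where a numeric measure has several candidates, proximity is the first criterion: "the assessment closest to the target day will be selected". Ties are then settled as follows: "If more than one assessment is at the same distance to the target day, the worst case will be selected". In its table of worst-case directions, the row beginning "Neurophysiological evaluations (NCV, CMAP, etc" makes the lower value the worse one. SAP 2.1.4.1 applies the same order, closest day and then worst case, to ECG and echocardiogram data.

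Baseline is defined separately. In SAP 2.1.1 it "is the last non-missing assessment obtained prior to the first administration of study drug". No worst-case rule is attached, and SAP Table 2-9 has no baseline window.

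SAP 2.8.8 plans descriptive summaries, listings and several plots. Some plots are drawn "excluding implausible post-baseline zero values"; the summaries carry no such exclusion.

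**The concern.** Measurements from one session share a date, so they are equally far from any target day. If they reach the analysis as separate records, the tie rule always operates on them and returns the minimum. Nothing comparable happens before dosing, so the two sides of a before-and-after comparison would be built differently.

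Nerve conduction is a primary safety endpoint in all three parts (Protocol 2.1, SAP 1.1.1). Protocol 3.8 ties neurophysiologic monitoring to the axonal degeneration seen in dogs. There is no placebo or active control (Protocol 3.4 and 3.6) in which an artefact of selection would show itself. A drop at the first post-dose visit is what a reader of these tables would be looking for, and the selection rule alone could produce one.

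**Working it through.** The documents state no figure on this point, so there is none to reproduce.

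**Inputs from the documents**
- k = 1, 2 or 3 measurements per nerve per session (Protocol 7.4.7). Actual counts are not given.
- Post-dose value: closest day, ties to the lower value (SAP 2.1.3).
- Baseline: last non-missing pre-dose value (SAP 2.1.1).

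**Assumptions**
- Each measurement is its own record, and baseline is one of them.
- Measurements within a session are independent and normal, with SD s_w.
- The session mean varies between sessions with SD s_b.
- The nerve does not change.

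**Step 1, mean shift.** Expected change = s_w × E[min of k standard normals], where E[min of k] = ∫ x·k·φ(x)·(1 − Φ(x))^(k−1) dx.
- k = 1: 0
- k = 2: −1/√π = −0.564
- k = 3: −3/(2√π) = −0.846

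Between-session noise does not alter this mean. A simulation of 1,000,000 stable subjects per scenario agreed: −0.564 to −0.566 for k = 2, and −0.841 to −0.848 for k = 3.

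**Step 2, share of stable children below baseline.** With s_b = 0, the baseline value and the k post-dose values are exchangeable. Baseline is the lowest of the k + 1 with probability 1/(k + 1), so the post-dose minimum lies below it with probability k/(k + 1). The rows with s_b > 0 are simulated.

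| s_b / s_w | k = 1 | k = 2 | k = 3 |
|---|---|---|---|
| 0 | 50% | 66.7% | 75.0% |
| 0.5 | 50% | 64.8% | 72.1% |
| 1 | 50% | 61.5% | 67.3% |
| 2 | 50% | 57.2% | 60.7% |

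**Step 3, as a percentage of the mean.** This needs a within-session CV, which the documents do not give. Illustration only: assumed CV × 0.564 or 0.846.

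| Assumed CV | k = 2 | k = 3 |
|---|---|---|
| 5% | −2.8% | −4.2% |
| 10% | −5.6% | −8.5% |
| 20% | −11.3% | −16.9% |

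**Step 4, later visits.** Every post-dose visit carries the same offset, so the expected difference between two post-dose visits is 0 when k is the same. If k moved from 3 to 2, the summary would rise by (0.846 − 0.564) s_w = 0.28 s_w with no change in the nerve.

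**Step 5, zeros.** A minimum selects any measurement recorded as zero, whatever the others show. If each had an assumed chance p of being recorded as zero, independently, the visit value with k = 3 would be zero with probability 1 − (1 − p)³: 5.9% for p = 2%, 14.3% for p = 5%, 27.1% for p = 10%.

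**Step 6, symmetric rule.** With the mean, the minimum or the last measurement used on both sides, the simulated expected change is 0.00 s_w in every scenario. With the mean on both sides, 50% of stable children fall below baseline.

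**The case against.** The strongest reply is that SAP 2.1.3 was not written for replicates within a session. SAP 2.1.2 introduces it as the way to handle multiple visits in a window, and its only example is unscheduled visits. Protocol 7.4.7 calls the replicates measurements and uses assessment for a whole neurophysiological examination. SAP 2.1.3 also lets the selected value be a derived one, so an earlier within-session step is compatible with the text. Further instructions sit in the Site Operations Manual, which is not among the documents. All of this stands, and it is why the point is conditional. It does not supply the missing rule. Elsewhere the SAP names a mean where it uses one (supine blood pressure in 2.3.2, QT duration in 2.8.5); 2.8.8 has no equivalent.

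Four stronger readings are tempting, and the documents do not support them.
- *The SAP definitely makes the visit value a minimum and baseline a single measurement.* Both depend on how the replicates are stored. The baseline session also allows three, and which same-day value counts as last is undefined.
- *Every change from baseline is biased.* SAP 2.8.8 does not name change from baseline, unlike 2.8.4 for laboratory data and 2.8.6 for vital signs. Table 2-9, which covers Parts 1 and 2, is titled for ulnar CMAP only.
- *A true decline could not be told from the artefact.* The artefact is one step. A continuing fall across visits would remain visible, both dose groups are affected alike if replicate counts are similar, and the listings and the plot of all raw data do not use the selected value.
- *The false fall has a known percentage size.* Step 3 rests on an assumed CV, and the 75% figure requires no between-session noise.

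**Conclusion.** The plan has a gap on a primary safety endpoint, and the only stated rule that could fill it is asymmetric. If replicates are separate records and baseline is one of them, by-visit summaries of a stable nerve step down once after baseline, by about 0.56 (two replicates) or 0.85 (three) within-session SD. With three replicates, about 61% to 75% of stable children would lie below baseline, for between-session SD from 2 down to 0 times the within-session SD, against 50% under a symmetric rule. If only one measurement is taken, or if replicates are first combined in the same way at all visits, the bias is zero.

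The size in percent cannot be derived from the documents. Growth or disease could mask the step or add to it. Zeros are a related exposure: under the minimum rule a zero replicate would enter the descriptive summaries, because SAP 2.8.8 removes implausible zeros only from some plots.

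**What to change.** In SAP 2.1.3 and 2.8.8, state that same-day replicates are reduced to one value per nerve and parameter before windowing, by one rule applied identically at baseline and at every visit. What removes the bias is using the same rule on both sides. The median is a reasonable choice because, with three replicates, it ignores a single failed stimulation.

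With two replicates the median is their mean, and one zero would halve the value. The handling of implausible zero replicates therefore has to be stated separately, for the summaries as well as the plots. Limit the worst-case tie rule to examinations on different days, list all replicates, and keep the lowest replicate as a sensitivity summary. If a within-session reduction already exists elsewhere, the SAP should cite it and confirm that it also applies at baseline.

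The cost is a short addition to the SAP and one derivation step. The downside is that the headline value is no longer the most pessimistic replicate; the sensitivity summary keeps that view available.
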